## STATISTICAL ANALYSIS PLAN for SIM-study

---

Characteristics	IV (n=xx)	SC (n=xx)	Overall (n=xx)
Sedatives/anxiolytics			
Drug(s) for acid related disorders			
Laxatives			
Antibiotics			
Diuretics			
Hearth medication Antihypertensives			
Other			
Total 24-hour oral morphine equivalents (OME) at inclusion mean (SD, min-max)			
Regular opioid dose at inclusion in OME, mean (SD, min-max)			
Total (regular and as needed) opioid use at inclusion in OME, mean (SD, min-max)			
Biochemistry      Mean (SD, min-max)			
CRP			
Hemoglobin			
WBC (and diff. counting)			
Platelets			
Sodium			
Potassium			
Calcium			
Creatinine clearance			
ASAT			
ALAT			
ALP			
Gamma GT			
INR			
Albumin			
Bilirubin			

Abbreviations: Q quartile, SD standard deviation, ESAS Edmonton Symptom Assessment System, EORTC-QLQ c30 European Organization for Research and Treatment of Cancer Core Quality of Life questionnaire, BMI body mass index, OME oral morphine equivalents, CRP C-reactive protein, WBC White blood cells, ASAT Aspartate aminotransferase, ALAT Alanine aminotransferase, ALP Alkaline phosphatase, INR International normalized ratio, GammaGT Gamma-glutamyl transferase.

### 3.3 Withdrawal/Follow-up

The status of eligible and randomized patients at trial end will be tabulated by treatment group according to:

- completed intervention and assessments.

- completed assessments but not intervention.
- completed intervention but not assessments.
- withdrew consent.
- lost to follow-up.

Time from randomization to treatment discontinuation and time from randomization to withdrawal/lost to follow-up will be presented in the CONSORT flow diagram.

### 3.4 Adherence and Protocol Deviations

#### 3.4.1 Adherence to Allocated Treatment

Adherence will be defined as the percentage of subjects who have completed the 48-hour intervention period.

#### 3.4.2 Protocol Deviations

The following pre-defined important protocol deviations are regarded to affect the efficacy of the intervention (See also Protocol Deviation Handling Plan):

- Subjects entered into the study even though they did not meet the entry criteria.
- Subjects who developed withdrawal criteria (from treatment or study) during the study but were not withdrawn.
- Subjects who received the wrong treatment or incorrect dose.
- Subjects who received an excluded concomitant treatment.
- Failure to register time from start of continuous IMP infusion until the last dose adjustment
- Withdrawn consent
- Other serious breaches according to the clinical trial protocol

The number (and percentage) of patients with major and minor protocol deviations will be summarized by treatment group with details of type of deviation provided. The patients that are included in the intention to treat analysis data set will be used as the denominator to calculate the percentages. No formal statistical testing will be undertaken.

### 3.5 Analysis Populations

The enrolled set will include all patients who have provided informed consent and have been included in the study database.

**The Full Analysis Set (FAS)** will be defined as all patients randomly assigned to a treatment group regardless of whether they received any study treatment after randomization.

**The Safety Analysis Set (SAS)** will include all patients that receive any study treatment after randomization.

**The Per Protocol (PP) population** will include all randomized patients who meet the study eligibility criteria, and complete the study according to protocol with no major protocol deviations affecting the treatment efficacy.

**The intention to treat (ITT) population** will include all patients who were randomly assigned to a treatment group, regardless of whether they complete the treatment as planned: Main outcomes will be analyzed based on intention to treat principle. Supplemental PP analyses will be based on patients who completed the 48-hour double blind period.

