## 2 Trial Methods

### 2.1 Trial Design

Comparison of morphine infusion combined with bolus doses, administered subcutaneously or intravenously. The study is a single center phase III randomized controlled double blind, double dummy trial with open label follow-up.

In order to ensure blinding during the double-blind phase of the study, each participant will have both an intravenously and a subcutaneously administered PCA pump. One pump will contain morphine, the other placebo (saline).

The intervention period is 48 hours

Open label follow-up is four weeks

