## **2.7 Timing of Main Analysis**

The main analysis is planned when all patients have completed the 48-hour intervention period. Pharmacokinetics will be analyzed when morphine serum concentration is measured for 20 study participants.

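### The SAP gives per-protocol rules in sections 3.5 and 4.5.5 that do not align, so the supplemental per-protocol result depends on which rule is followed

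*SAP*

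**What the plan says.** Three places in the SAP decide who enters a PP analysis.

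- **Section 3.5, definition of the PP population.** It "will include all randomized patients who meet the study eligibility criteria", and these patients must also "complete the study according to protocol with no major protocol deviations affecting the treatment efficacy".
- **Section 3.5, last sentence.** "Supplemental PP analyses will be based on patients who completed the 48-hour double blind period". No other condition is given.
- **Section 4.5.5 (missing data for outcome b).** Patients judged not to have pain control when the 48-hour blinded treatment ends are left out of PP analyses and kept in ITT analyses.

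Section 3.4.2 supplies the deviations. It says that its listed "pre-defined important protocol deviations are regarded to affect the efficacy of the intervention". The list includes entry despite not meeting the criteria, "Subjects who received the wrong treatment or incorrect dose", and use of an excluded concomitant treatment. The same section then changes vocabulary: "The number (and percentage) of patients with major and minor protocol deviations will be summarized by treatment group". It also refers to a separate Protocol Deviation Handling Plan. Section 3.5 makes ITT the basis for the main outcomes.

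**The concern.** A PP analysis is normally run to see whether the treatment comparison changes once patients with efficacy-relevant deviations are set aside. The definition in section 3.5 would do that. The last sentence of the section, taken as written, would not do so for patients who deviate but still finish 48 hours. Two statisticians could build different PP sets and both cite section 3.5.

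This has some weight because section 4.4.3 plans no sensitivity analyses for the primary outcome, and section 3.4.2 only tabulates deviations, without testing. The PP analysis is therefore the one planned comparison that could show whether deviations matter to the route comparison. If its membership is open, the choice could be made after unblinding.

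The rule in section 4.5.5 raises a different problem, because it selects patients on a result of treatment and not on conduct. Outcome b is the share of patients without adequate relief at 48 hours. If lack of pain control there means the same as lack of adequate relief, the exclusion removes every patient who has the outcome, and the PP share is zero in both arms by construction.

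**Working it through.** **Reproducing the plan's own figure.** Section 4.9 assumes a 12 h difference, SD 12 h, two-sided 5% and 90% power. The standardised difference is 12/12 = 1. The exact t-test needs 22.02 per arm, rounded up to 23, where power is 91.2%. The SAP states 23, so the figure reproduces. Allowing for 25% dropout, 23/0.75 = 30.7, or 31 against the stated 30, a difference of one patient per arm. None of this decides the point, which rests on wording.

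**The rules side by side.** Rule A is the PP definition in section 3.5, rule B its last sentence, rule C section 4.5.5.

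| Patient | Rule A | Rule B | Rule C |
|---|---|---|---|
| Completed 48 h, did not meet entry criteria | Out | In | Silent |
| Completed 48 h, wrong treatment or dose | Out if classed as major | In | Silent |
| Completed 48 h, excluded concomitant treatment | Out if classed as major | In | Silent |
| Completed 48 h, no deviation, no pain control at 48 h | In | In | Out |
| Withdrew consent before 48 h | Out | Out | Silent |

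1. Row 1 conflicts without any further assumption, because eligibility is an explicit condition of rule A and absent from rule B.
2. Rows 2 and 3 conflict once the deviations called important in section 3.4.2 count as major in section 3.5. The SAP never makes that link; the Protocol Deviation Handling Plan may.
3. Row 4 conflicts because neither rule in section 3.5 mentions pain control. The row assumes that finishing with inadequate relief is not itself a deviation; section 3.4.2 does not list it as one.
4. Row 5 shows where rules A and B agree: patients who leave before 48 hours are out under both.

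**Size.** The effect on the PP estimate would be the number of patients in rows 1 to 4 combined with how far their outcomes differ from the rest. The SAP gives neither a deviation rate nor an expected share without pain control, so this cannot be computed.

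**The case against.** The strongest reply is that the sentences in section 3.5 can be read together. The PP population is a defined term, so its eligibility and deviation conditions carry over to anything called a PP analysis, and the last sentence only says which completion counts. This is plausible and close to the fix below. But the SAP does not say it. Section 3.4.1 also uses 48-hour completion by itself as the adherence measure, so a plain completer analysis is an equally available reading. The harmonised reading does not account for section 4.5.5 either.

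A reader might go further in four ways that the document does not support.

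- **Study completion as four weeks.** Section 2.1 says "Open label follow-up is four weeks", so a reader might infer that the PP set drops patients who die or leave after the 48-hour outcomes are recorded. The wording is loose enough to allow it. The context points the other way: section 4.2 defines the primary outcome within 48 hours, section 3.4.1 ties adherence to 48 hours, section 2.7 says "The main analysis is planned when all patients have completed the 48-hour intervention period", and the last sentence of section 3.5 itself names the 48-hour period.
- **A loss of power.** Suppose one or two of 23 completers per arm received the other route. The difference falls to 12 × (1 − 2/23) = 10.96 h or 12 × (1 − 4/23) = 9.91 h. At SD 12 h, power is 86% or 78%; with the SD of the mixed group (12.25 or 12.47 h) it is 84% or 75%. The arithmetic is sound but the counts are invented, and power is not the measure by which a supplemental analysis stands or falls.
- **A completer analysis that says nothing about deviations.** This is too strong. Consent withdrawn within the 48 hours still leads to exclusion. Where the time to last adjustment was not registered and the outcome is therefore missing, section 4.4.2 removes the patient from the primary-outcome analyses. What stays unresolved is rows 1 to 3 of the table.
- **Wrong-route patients by name.** Section 3.4.2 speaks of wrong treatment. Including route is reasonable, since route is what separates the arms, but it is an inference.

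**Conclusion.** The point holds as a misalignment between stated rules that select different patients. For ineligible completers it follows directly from the text. For completers with wrong treatment or dose, or an excluded treatment, it assumes that the deviations listed in section 3.4.2 are classed as major. Section 4.5.5 adds an outcome-based exclusion found in neither rule of section 3.5.

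The consequence is small. The ITT analysis of the main outcomes and the decision rule in section 2.4.3 are untouched; only the supplemental PP result is open. No numerical size can be given. This is a worthwhile clarification, not a threat to the trial's conclusion.

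**What to change.** Adopt one PP definition: randomised patients who met the eligibility criteria, completed the 48-hour double-blind period, and had none of the section 3.4.2 deviations classed as major, with that classification fixed before unblinding. In detail:

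- In the section 3.5 definition, replace completion of the study with completion of the 48-hour double-blind period.
- Change the last sentence of section 3.5 to say that supplemental PP analyses use the PP population.
- State which section 3.4.2 deviations are major, or refer to the Protocol Deviation Handling Plan if it already does so, and use one term throughout.
- Remove the PP exclusion of patients without pain control from section 4.5.5.

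The cost is SAP wording only, with no new data or procedures. The PP set may be a few patients smaller than a pure completer set.

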### **3.5.1 Pharmacokinetic (PK) subgroup analysis set:**

A subgroup of 20 participants that are enrolled in the study and meet eligibility criteria including the serum measurement specific criteria of Hb>9, and consent to blood sampling are considered for PK analyses.

The PK concentration population includes all study participants who have serum samples after bolus dose available for analysis.. The PK analysis population will be defined as all subjects who have PK data from minimum three concentration measurements.

## **4 Outcome Definitions**

### **4.1 General Definitions and Derived Variables**

#### **4.1.1 NRS – Numeric Rating Scale**

NRS is a widely used, standard one-dimensional scale from 0 to 10 for patient self-reporting of pain (Breivik et al., 2008). NRS is collected as part of ESAS at 0, 12, 24, 36, and 48 hours. Exact recording time is registered. NRS is also recorded before and after any bolus dose administration. A change of NRS of 2 or more after a bolus dose is considered as clinically significant change. A mean NRS score difference of 1-2 is typically considered clinically significant when treatment arms are compared.

#### **4.1.2 ESAS - Edmonton Symptom Assessment System**

A questionnaire used to rate the intensity of nine common symptoms experienced by cancer patients, including pain, tiredness, nausea, depression, anxiety, drowsiness, appetite, well-being and shortness of breath on an 11-point numeric rating scale mimicking the NRS scale (Bruera et al., 1991).

#### **4.1.3 EORTC QLQ-C30 - European Organization for Research and Treatment of Cancer Quality of Life Questionnaire Core 30**

Health-related QOL will be assessed using the cancer-specific EORTC QLQ-C30 (Aaronson et al., 1993), which contains 30 items across 5 functional scales, 9 symptom scales and a global health

status/QOL scale (Table 3). Items 1-28 have 4 response levels (not at all, a little, quite a bit, and very much) and items 29 and 30 are scored on a 7-point numeric rating scale. A summary score of EORTC QLQ-C30 will be calculated from the mean of the 15 EORTC QLQ-C30 subscales.

Descriptive statistics of observed values for the subscale scores of EORTC QLQ-C30 will be presented by treatment group.

**Table 3 Definition of Subscale Scores of EORTC QLQ-C30**

Subscale	Number of questions	Question range	Individual Items
Physical functioning	5	3	1-5
Role functioning	2	3	6-7
Emotional functioning	2	3	21-24
Cognitive functioning	4	3	20, 25
Social functioning	2	3	26-27
Fatigue	3	3	10, 12, 18
Nausea and vomiting	2	3	14-15
Pain	2	3	9, 19
Dyspnea	1	3	8
Insomnia	1	3	11
Appetite loss	1	3	13
Constipation	1	3	16
Diarrhea	1	3	17
Financial difficulties	1	3	28
Quality of life	2	6	29-30

*Abbreviations: EORTC QLQ-C30 = European Organization for Research and Treatment of Cancer Quality of Life Questionnaire Core 30*

*Every dimension (column 1) has a specific number of items assigned that are used to obtain the score. For instance, for Global health status (QL2) dimension, there are two items (number 29 and 30) used to obtain the score. The raw score for each dimension is calculated by averaging all the items assigned to the specific dimension.*

#### **4.1.4 Opioid side effect score**

A questionnaire used to rate the intensity of 10 common symptoms experienced when on opioid treatment, including nausea, vomiting, constipation, drowsiness, disorientation, hallucinations, and spasticity on an 11-point numeric rating scale mimicking the NRS scale will be used (Fallon et al., 2022)

#### **4.1.5 Global impression of change**

The Patient Global Impression of Change (PGI-C) is a single item designed to capture the subject's perception of change in overall symptom severity from randomization until the time of completion

---

(Guy, 1976). Change in severity is captured using a 7-point scale: 1-Very much improved, 2-Much improved, 3-Minimally improved, 4-No change, 5-Minimally worse, 6-Much worse, 7-Very much worse. The number and percentage of patients with each PGI-C score will be summarized by treatment group for the ITT population.

## **4.2 Primary Outcome Definition**

- a) The time (hours and minutes) from start of continuous infusion until the last dose adjustment within the 48-hour period.

## **4.3 Secondary Outcomes Definitions**

- b) The share of patients not reaching adequate pain relief within 48 hours.
- c) Comparison of pain score every 12 hours during the 48 hour period.
- d) Number of bolus doses the first 24- and 48 hours (assessed every 12 hours.)
- e) Time from bolus administration of morphine to clinically significant pain relief (reduction of 2 on NRS 0-10)

### **Pharmacokinetic study**

- f) Difference in the key pharmacokinetic parameters  $T_{max}$ ,  $C_{max}$ , and  $AUC_{0-60}$  after SC and IV administration of morphine bolus doses in steady state\* morphine infusion in palliative cancer patients. (\*>24 hours after start of infusion and >2 hours since last bolus dose.)

## **Analysis Methods**

### **4.4 Methods for Primary Outcome**

**The time (hours and minutes) from start of continuous infusion until the last dose adjustment within the 48-hour period. (Outcome a)**

As primary analysis, an independent samples t-test will be used for comparison of primary outcome between SC and IV groups. Since the outcome is censored at 48 hours, the same comparison will also be performed by a tobit regression model. In the case of violation of model assumptions, a suitable transformation of data or a non-parametric alternative will be considered for sensitivity analysis.

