### **2.2 Randomization**

The allocation ratio between treatments is 1:1 with no stratification. The randomization will be performed by using a computer-generated list of blocks of 6-8 patients. The randomization process is described in detail in *SIM-Study Procedure Manual version 1.3, 07.07.22*. Details of the randomization including the final random allocation list are held securely and unavailable to unauthorized trial personnel. Sequentially numbered, opaque, sealed envelopes containing information about patient allocation are located at the Department of Palliative Medicine for emergency and unblinding after 48-hour intervention period.

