## 4.9 Sample size

The estimation of sample size is performed for primary outcome, time from start of continuous infusion until the last dose adjustment within the 48-hour period, and is based on the following assumptions: normal distribution within each treatment arm, difference in time from start of infusion to final dose adjustment between the IV and SC treatment arm of minimum 12 hours (assumed clinically significant), and SD of 12 hours in each arm. To show that the difference between the groups is statistically significant at the significance level of 5% with 90% power, using a two-sided independent samples t-test, the minimum number of patients is estimated to be 23 in each arm, total 46. Expecting a 25% dropout rate, 30 subjects need to be included in each group.

---

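### The primary comparison uses no baseline covariate, so precision is forgone and chance imbalance left uncorrected if baseline pain and opioid dose, both already collected, are prognostic

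*SAP*

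**What the plan says.** - **Decision analysis.** Section 4.4 states that "an independent samples t-test will be used for comparison of primary outcome between SC and IV groups". Because the outcome is censored at 48 hours, "the same comparison will also be performed by a tobit regression model". No covariate is named for either model in sections 4.4 to 4.4.4. Section 4.4.3 lists no sensitivity analysis and section 4.4.4 no subgroup analysis.
- **Randomisation.** Section 2.2: "The allocation ratio between treatments is 1:1 with no stratification". Neither starting pain nor starting opioid dose is balanced by design.
- **Baseline data.** Section 4.1.1: "NRS is collected as part of ESAS at 0, 12, 24, 36, and 48 hours". Table 2 lists baseline ESAS by element and "Total 24-hour oral morphine equivalents (OME) at inclusion", plus two further baseline OME rows (regular dose; regular plus as-needed).
- **Imbalance.** Section 3.2 says baseline characteristics will be tested for significance and the clinical importance of any imbalance noted. No analysis of the primary outcome follows from that note.
- **Sample size.** Section 4.9 assumes a "difference in time from start of infusion to final dose adjustment between the IV and SC treatment arm of minimum 12 hours" and an SD of 12 hours, to be "statistically significant at the significance level of 5% with 90% power", "using a two-sided independent samples t-test". This gives 23 per arm, and 30 per arm after 25% dropout.
- **Covariates elsewhere.** The pharmacokinetic mixed model in section 4.6.1.3 has fixed effects for dose, age, sex and weight.

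**The concern.** The primary outcome is the time to the last dose adjustment within 48 hours. It is reasonable, though not shown in the SAP, to expect that patients who start with more pain or a higher opioid requirement take longer to titrate. If so, part of the 12-hour SD is explained by values recorded before treatment, and an unadjusted test leaves that part in the error term. With about 23 evaluable patients per arm and no stratification, an appreciable chance difference in either variable is also possible.

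There is a procedural side too. The plan will run baseline significance tests and comment on imbalance, but it gives no route from that comment to an analysis. If an imbalance appears, the team must either leave the estimate alone or choose covariates after seeing data. Fixing the covariates beforehand removes that choice.

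**Working it through.** **1. The plan's own figure.** Inputs from section 4.9: difference 12 h, SD 12 h, two-sided 5%, 90% power. For a two-sample t-test with n per arm, the noncentrality is 12 / (12 × √(2/n)) on 2n − 2 degrees of freedom.
- n = 22: noncentrality 3.317, power 89.97%.
- n = 23: noncentrality 3.391, power 91.2%.

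The stated 23 per arm reproduces. With 25% dropout, 30 enrolled leave 30 × 0.75 = 22.5 evaluable per arm, which is used below.

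**2. Unadjusted analysis at 22.5 per arm.** Degrees of freedom are 43 and t(0.975) = 2.017.
- Half-width of the 95% CI: 2.017 × 12 × √(2/22.5) = 7.22 h.
- Power: 90.6% for a true 12 h difference, 69% for 9 h.

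**3. Adjusted analysis with two covariates.** R² is an assumption, so a range is shown. Two costs are charged:
- error degrees of freedom fall to 45 − 4 = 41, with t(0.975) = 2.020;
- the variance of the treatment estimate is multiplied by 1 + 2/(2n − 5) = 1 + 2/40 = 1.05, because the two slopes are estimated.

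Half-width = 2.020 × 12 × √(1.05 × (1 − R²)) × √(2/22.5). Power uses the noncentral t with the same standard error.

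| Analysis | CI half-width (h) | Power, 12 h | Power, 9 h |
|---|---|---|---|
| Unadjusted | 7.22 | 90.6% | 69% |
| Adjusted, R² = 0 | 7.40 | 89.2% | 67% |
| Adjusted, R² = 0.05 | 7.22 | 90.6% | 69% |
| Adjusted, R² = 0.09 | 7.06 | 91.8% | 71% |
| Adjusted, R² = 0.16 | 6.79 | 93.7% | 74% |
| Adjusted, R² = 0.25 | 6.41 | 95.8% | 79% |

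The factor 1.05 × (1 − R²) equals 1 at R² = 1 − 1/1.05 = 0.048. The loss of two degrees of freedom moves break-even only slightly, to about 0.05.

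**4. Chance imbalance.** The standardised difference between arms in one baseline covariate has standard error √(2/n): 0.298 at 22.5 per arm and 0.258 at 30 per arm. By the normal approximation, a difference above 0.5 SD has probability about 9% at 22.5 per arm and 5% at 30 per arm. If the covariate has correlation r with the outcome, such a difference shifts the unadjusted estimate by r × 0.5 × 12 h. That is 1.8 h at r = 0.3, 2.4 h at r = 0.4 and 3.0 h at r = 0.5. These correlations are also assumptions.

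**The case against.** The strongest reply is that nothing here is wrong. Under 1:1 randomisation the t-test is unbiased and keeps its level, it is the test on which section 4.9 is based, and it reaches the planned power without covariates. All of that stands. A reader might infer that the primary analysis is invalid or biased; the document does not support that reading. Chance imbalance is not bias, and the t-test's interval already allows for it on average. A 2.4 h shift lies well inside the 7.22 h half-width and needs both a 9% event and an assumed correlation of 0.4.

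A reader might also infer that precision is certainly lost, or that adjustment always shortens the interval. Neither follows. The SAP gives no figure for how well baseline pain or OME predicts the outcome. All patients enter with unsatisfactory pain control, which may narrow the spread of baseline pain. Below R² of about 0.05 adjustment gains nothing or costs a little, and at 0.09 the gain is only about 1 point of power and 9 minutes of half-width.

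Finally, adjustment could be added as a sensitivity analysis, leaving the powered test in place. That would address imbalance, but any gain in precision would not reach the decision rule in section 2.4.3. The possible loss is small and bounded, so this reply does not defeat the change.

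**Conclusion.** The point holds conditionally, as a cheap improvement. The textual part is certain: no covariate in either primary model, two relevant baseline measures already collected, no stratification, and no analysis attached to a noted imbalance. The size of the benefit is not known from the SAP. At 22.5 evaluable per arm and SD 12 h it ranges from a loss of about 1.5 points of power at 12 h (2 points at 9 h) when the covariates explain nothing, to a gain of about 5 points at 12 h and 10 points at 9 h when they explain a quarter of the variance. Over the same range the half-width changes from 0.18 h wider to 0.81 h narrower (7.40 and 6.41 h against 7.22 h). The calculation takes the normal linear model and the SD from section 4.9 as given. The trade favours adjustment if R² above about 0.05 is thought likely, which is a judgement for the trial team.

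**What to change.** Amend section 4.4 before unblinding:

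- Make the primary analysis a linear regression of the outcome on treatment, hour-0 ESAS pain NRS and one baseline OME variable. Name which of the three OME rows in Table 2 is meant and its scale, for example total 24-hour OME at inclusion on the log scale.
- Use the adjusted mean difference and its 95% CI for the decision rule in section 2.4.3.
- Put the same two covariates in the tobit model, and keep the unadjusted t-test as supportive.
- State a simple imputation rule for a missing baseline value, for example the mean over both arms, so that no randomised patient is dropped because a covariate is missing.
- State that the covariates are fixed in advance and not chosen from the baseline significance tests in section 3.2.

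The cost is SAP wording and two degrees of freedom, with no new data. If the covariates prove not to be prognostic, the price is about 1.5 points of power at 12 h and 2 points at 9 h.
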